
## 2. Objectives and Hypotheses

[figure not shown]
Our long-term goal is to understand the determinants of children’s individual susceptibility to environmental food cues and cued eating to develop interventions that reduce childhood obesity. Our overall objective is to determine how media multi-tasking affects attention to peripheral food cues and overeating, and whether it is possible to intervene on this proposed pathway. We have two central hypotheses. The first is that engaging in media multi-tasking increases attention to peripheral cues and thereby makes children more susceptible to environmental food cues (e.g., food advertising, sight or smell of food) that leads to cued eating in the absence of hunger. The second is that attentional training that improves sustained attention protects children against attention to peripheral food cues and therefore makes them less susceptible to cued eating.

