#### 4. Analysis

**Describe any qualitative tests and measures as well as quantitative methods:**

Our primary outcomes of interest will be  $\Delta$  first fixation duration to peripheral cues,  $\Delta$  cumulative fixation to peripheral cues, and  $\Delta$ EAH and our primary exposures will be the multi-task vs. control condition and the sustained attention task vs. control. We will first assess main effects of the acute tasks by using multivariable linear regression to fit  $\Delta$  attention eye-tracking metrics on  $\Delta$ EAH. Cohen's power calculation for regression, and setting alpha to  $P < .05$ , two-tailed, we calculated 80% power to detect a moderate effect size ( $f^2 = .15$ ) for main effects. To test for moderation, we will then repeat the main effects models stratifying the sample by the median of usual media multi-tasking. We will conduct a formal test for interaction by repeating the main effects models on the entire sample with the acute task, usual media multi-tasking, and the product of the acute task and usual media multi-tasking as the independent variables of interest. A Wald test on the product term  $P < 0.10$  will be considered evidence of a statistically significant interaction.

To examine the effects related specifically to food images, we will repeat all analyses using first fixation bias and cumulative fixation bias to food cues as our outcomes of interest. A first fixation bias to food cues was calculated by computing the difference between first fixation duration to food and animal images. A positive value represents that a child looked longer the first time they fixated a food versus toy distractor. A cumulative gaze duration bias to food cues was calculated by computing difference between cumulative fixation duration to food versus toy animal distractors. A positive number indicates that a child spent more total time looking at food versus toy distractors.

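### Product terms with P < 0.10 are labelled statistically significant across about ten unadjusted tests; they should be reported as exploratory flags

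*Combined protocol and SAP*

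**What the plan says.** All the relevant text is in section 4 (Analysis) of the combined protocol and SAP.

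- **Outcomes.** Three primary outcomes are named, each as a change: "first fixation duration to peripheral cues, $\Delta$ cumulative fixation to peripheral cues, and $\Delta$ EAH".
- **Contrasts.** There are two: "our primary exposures will be the multi-task vs. control condition and the sustained attention task vs. control".
- **Main effects.** The power sentence sets a two-tailed 0.05 level.
- **Moderation.** The main-effects models are first repeated above and below the median of usual media multi-tasking. The formal test then uses the whole sample and adds "the product of the acute task and usual media multi-tasking as the independent variables of interest". The decision rule is that a Wald P below 0.10 for the product term "will be considered evidence of a statistically significant interaction".
- **Food-specific outcomes.** The plan then states: "we will repeat all analyses using first fixation bias and cumulative fixation bias to food cues as our outcomes of interest".

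Section 2 (Objectives and Hypotheses) says "We have two central hypotheses": that media multi-tasking increases susceptibility to food cues, and that attention training protects against it. Neither mentions usual multi-tasking as a moderator. The document nowhere adjusts for multiplicity, ranks the interaction tests or labels them exploratory.

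**The concern.** Moderation is judged at a level twice as lenient as the main effects, and the result is still called statistically significant. The rule applies separately to every outcome and contrast, so the chance of some false declaration grows with the number of tests. Nothing in the plan tells a reader to discount an isolated positive.

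What is at stake is the claim that the trial can make. A product term with P of, say, 0.08 on one of five outcomes could be reported as a statistically significant finding about which adolescents are susceptible to multi-tasking, or which benefit from training. Section 1 cites a young-adult study in which training helped heavy multi-taskers more, so a chance result in that direction would be easy to read as confirmation.

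**Working it through.** **The plan's own figure.** The document gives no error rate for the interaction tests. The nearest reproducible figure is the statement in section 4 of 80% power for |r| of 0.27 with 107 participants at two-sided 0.05. By Fisher's z, power = Φ(atanh(0.27) × √(107 − 3) − 1.96) = Φ(0.277 × 10.198 − 1.96) = 80.6%. The figure reproduces. It concerns correlations with EAH, not product terms.

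**Inputs from section 4.** The level per product term is 0.10. There are 3 primary outcomes, 2 further food-bias outcomes and 2 contrasts.

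**Number of tests (inferred; the plan does not state it).** Primary: 3 × 2 = 6. All: (3 + 2) × 2 = 10. The median-split models are further unadjusted looks and are not counted here.

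**Expected false declarations if no interaction is real.** 6 × 0.10 = 0.6 and 10 × 0.10 = 1.0. These means do not depend on the correlation between tests.

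**Chance of at least one, independent tests.** 1 − 0.9^6 = 46.9% and 1 − 0.9^10 = 65.1%.

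**Chance of at least one, correlated tests.** The document gives no correlations, so a range is assumed. Both contrasts subtract the same control visit. With equal variances and equal correlation ρ between visits, the covariance of the two differences is σ²(1 − ρ) and each variance is 2σ²(1 − ρ), so their correlation is 0.5. A multivariate-normal simulation with 1,000,000 draws, this 0.5, and a common correlation between outcomes gives:

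| Outcome correlation | Ten tests | Six primary tests |
|---|---|---|
| 0 | 62% | 44% |
| 0.3 | 58% | 42% |
| 0.5 | 52% | 39% |
| 0.6 | 48% | 37% |
| 0.8 | 38% | 31% |

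A common correlation across all five outcomes is a simplification. A structured alternative correlates the two fixation measures at 0.3 to 0.9, the two bias measures likewise, and EAH with each at 0.2. Ten tests then give about 60%, falling to 50%.

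**If one joint test per outcome were used.** Five tests give 1 − 0.9^5 = 41.0%.

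**Is the 0.10 level the whole problem?** No. Ten independent tests at 0.05 still give 1 − 0.95^10 = 40.1%. The number of tests and the label matter as well as the level.

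**The case against.** Several points on the other side have force.

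**A 0.10 level is defensible for an interaction test.** Such tests have low power, and the level is declared in advance. This stands for a single test used as a flag. It does not justify calling any of about ten unadjusted results statistically significant.

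**The testing is bounded.** A reader might infer an open-ended subgroup search. The documents do not support that: there is one named moderator, one form of test, named outcomes and two named contrasts. That is why the tests can be counted.

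**The count of ten is not certain.** The main-effects sentence speaks of regressing the attention changes on the EAH change, which leaves the exact models unclear. Ten is the natural reading of three plus two outcomes by two contrasts, but it remains an inference.

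**The outcomes may be highly correlated.** All four attention measures come from the same Tetris eye-tracking session, and the bias scores are built from the same fixation durations. High correlations are therefore possible, at least among those four, and they lower the chance of any false positive. They do not lower the expected number.

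**Moderation may be an aim.** Its absence from the two hypotheses in section 2 suggests a secondary question. However, section 1 gives a directional rationale, section 3 refers to Aims 1-3 without listing them, and a figure in section 2 is not shown. Its status cannot be settled from the text.

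**A formal adjustment would be costly and lopsided.** Holm over six tests starts at 0.05/6 = 0.0083. Treating a product term as a simple correlation with 107 participants, power for r = 0.27 falls from 88% at 0.10 to 57% at that first step, while the main effects would remain unadjusted. This stands, and is why adjustment is optional in the change proposed.

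**Conclusion.** The concern holds in a bounded form. Under a complete null, the written rule yields on average 1.0 false declaration across ten tests, or 0.6 across the six on primary outcomes. The chance of at least one among ten is 65% if independent and about 62% to 48% with a shared control and outcome correlations of 0 to 0.6. For the six it is 47%, and about 44% to 37%. Higher correlations lower these figures further. Even the smaller ones are too large for a result carrying the words statistically significant.

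Two stronger readings are tempting. A reader might infer that a false moderation claim is more likely than not. That requires counting all ten tests, no real interaction in any of them, and a common outcome correlation no higher than about 0.55; for the six primary tests the chance is below half in every case examined. A reader might also take the mean of 1.0 to say that the study will report one false moderator. Over outcome correlations of 0 to 0.6, the chance of none among ten is about 38% to 52%.

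The results rest on the inferred count, the complete null and the assumed correlations. The main-effect analyses are not affected.

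**What to change.** Replace the decision sentence in section 4 with wording to this effect: a product term with P < 0.10 will be treated as a flag for exploratory moderation and will not be described as statistically significant; all ten product terms will be reported with estimates and 95% confidence intervals, together with the number tested; no confirmatory claim of moderation will be based on them. If the models actually planned give a different number of tests, state that number.

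The cost is one or two sentences. The study gives up the ability to call an interaction statistically significant at 0.10. No test, estimate or data collection is lost. Holm adjustment could be added if the investigators want a confirmatory moderation claim, but it is not required.

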## 1. Introduction and Background

In the Children’s multimedia study, we propose to investigate the effects of media multi-tasking on child obesity. The modern obesogenic environment is replete with cues to eat. Environmental food cues stimulate brain reward regions and lead to excess consumption independent of hunger levels (1). This cued eating is partially mediated by the amount of attention given to food cues. For example, children who spend more time looking at food cues consume more calories than children who do not (2). We propose that the prevalent practice of media multi-tasking—simultaneously attending to multiple electronic media sources—increases attention to peripheral food cues and subsequent cued eating and thereby plays an important role in the development of obesity. Neural networks are responsible for controlling attention to peripheral cues. The dorsal and ventral orienting networks control the shifting and focusing of attention, and the frontoparietal network controls the filtering of peripheral cues in the environment (3-5). Media multi-tasking is known to increase orienting and decrease the filtering abilities associated with these networks (6-8). By this mechanism, we propose that media multi-tasking increases obesity risk by increasing attention to peripheral food cues. Current efforts to address obesity ignore this prevalent risk behavior. Fortunately, it is possible to improve the functioning of the attentional networks through attention modification training (9); thus this research examines the hypothesis that attention modification training can decrease the amount of attention children give to food cues.

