
## **Attentional training reduces attention to peripheral environmental cues.**

It is possible to decrease the amount of attention given to peripheral food cues through attention modification training (36-38). Research in adults (36) and children (9) support our contention that one-session attention modification training can decrease immediate consumption. In addition, a study of a large sample of undergraduates showed that activation of executive control using the Stroop Task reduced the amount of attention given to food cues in a subsequent dot-probe paradigm, suggesting that acute manipulations of attention can have immediate effects on the amount of attention given to food cues (39). This is consistent with the robust research in the anxiety domain that has shown one-time attention modification training can reduce the amount of attention given to threatening cues (40). To date, however, there have been no studies that have looked at the effect of attention modification training that improves sustained attention (AMT-S) on the amount of attention given to food cues. AMT-S may be particularly effective at reducing attention to peripheral food cues in children, because it is based on a translational neuroscience approach in which the therapeutic action directly targets the brain’s attentional networks, rather than specific types of cues. For example, research with neglect patients showed that AMT-S training produced increased activation in the superior parietal cortex and right and left frontal areas and anterior cingulate cortex. These brain regions have been associated with all three attentional networks (41,42). This generalized attention training may be the most effective given the heterogeneity of food cues in our current obesogenic environment. In addition, AMT-S interventions are uniquely promising because the mechanisms associated with sustained attention are the opposite of the automatic, poorly filtered attention thought to underlie the negative effects of media multi-tasking (43). For example, sustained attention is the ability to focus and self-sustain mindful, conscious processing of task-relevant stimuli that would otherwise lead to habituation and subsequent distraction to extraneous stimuli (44). Consistent with this suggestion, a short-term intervention that has been shown to improve sustained attention in undergraduates (45) has also been shown to reduce the maladaptive attentional processing associated with media multi-tasking. The study conducted with a large sample of young adults showed that AMT-S improved performance on a battery of attention tasks - including filtering and distractibility - in both high- and low-usual media multi-taskers, but this effect was greater for high media multi-taskers (43).

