**Attention to peripheral cues.** Immediately following the multi-tasking experimental manipulation, children will play a game of Tetris that measures attention to peripheral cues using eye-tracking. On either side of the game screen are pictures of food and animals that change periodically. Study staff will set up children with the task, provide directions, have children do a practice trial game, and clarify directions if necessary. The food cue is chosen at random on a game-to-game basis. To encourage gameplay concentration, children are encouraged to complete as many games as possible within 10 minutes. This game has high ecological validity because it mimics Internet advergames that are used to advertise products to children (2). We will use established eye-tracking metrics to measure attention to food cues. The amount of attention given to peripheral cues while playing the video game Tetris will be calculated for each participant after they completed each experimental condition. Areas of interest will be created around distractor images, defined as the area of the image, 250 X 250 pixels. First fixation duration will be measured as the average amount of time an adolescent spent fixating a distractor the first time that they looked at it. Cumulative fixation duration will be calculated as the total amount of time participants spent fixating distractors, summed over all fixations. For both measures, a fixation duration will be defined as any stationary period lasting at least 100 milliseconds. Eye-tracking will be recorded using the EyeLink 1000 Plus (SR Research, Ottawa, Ontario, Canada). The EyeLink is a robust desktop configuration that also includes facial recognition software to monitor head movements. This ability to compensate for head movements is particularly useful because it assures that when participants look away from the stimulus and then return to it, the system will automatically reacquire the eye. Critically, the video used to track the eyes is not saved and the person's likeness is never recorded.

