## 8. Deception

Does any part of this study involve deception or withholding of information from participants?

Yes       No

If Yes, provide an explanation which addresses the following:

- A description of the deception being used
- Why the deception is necessary
- A plan for debriefing, or providing subjects with the pertinent information after participation

We will not completely disclose the purpose of the main study or the purpose of the sub-study to participants in order to avoid bias. This may lead to the participants feeling distressed about being deceived or distrustful of scientific research. In order to address the risks associated with not completely disclosing the research aims of the study, we will send a letter to parents that explains the full purpose of the study when the study is complete. We will explain that we did not reveal the study purpose because we thought that such knowledge might have influenced their children's behavior. We will provide our contact information so that parents and/or their children can discuss the study further if they desire. These procedures will also be followed for the sub-study.

The full debriefing of the main study reveals the objective of the Tetris game, which is to assess how much attention participants pay to the peripheral food cues as they play Tetris. However, because the Tetris game is used for the same purpose in the sub-study, fully debriefing participants after they finish the main study but before they complete the sub-study (as is our current protocol) may affect their responses in the Tetris game during the sub-study. For this reason, those participants in the main study that choose to participate in the sub-study will be debriefed of both studies after they complete the sub-study.

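### The stated target is attention to food cues, but every planned gaze outcome is pooled over food and animals or is food minus animal; absolute attention to food is not an outcome

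*Combined protocol and SAP*

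**What the plan says.** Several sections name food as the target. Section 2 states: "Our overall objective is to determine how media multi-tasking affects attention to peripheral food cues and overeating". Section 1 gives the training hypothesis as whether "attention modification training can decrease the amount of attention children give to food cues". Section 8 describes "the objective of the Tetris game, which is to assess how much attention participants pay to the peripheral food cues".

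The measurement text in the Approach part of section 3 (Attention to peripheral cues) starts from the same place: "We will use established eye-tracking metrics to measure attention to food cues". But the display is mixed: "On either side of the game screen are pictures of food and animals that change periodically". The metrics are not split by image type: "Areas of interest will be created around distractor images". First fixation duration is an average over distractors, and cumulative fixation duration is a total over distractors.

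Section 4 makes the changes in these two metrics, described there as fixation to peripheral cues, the primary gaze outcomes. To examine food images specifically it adds: "we will repeat all analyses using first fixation bias and cumulative fixation bias to food cues as our outcomes of interest". Both bias scores are defined as food minus the non-food comparison image.

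On mechanism, the part of section 1 on attentional training says that training acts on "attentional networks, rather than specific types of cues".

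**The concern.** Counting the gaze outcomes gives two pooled over image type, two that are differences between image types, and none for food alone. The quantity named in the objective, how much children look at food, is therefore not estimated directly by any of the four.

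This matters because of the mechanism the plan proposes. If training improves attention generally, looking at food and at animals should fall together. The analysis set aside for food images is then expected to be null even though the hypothesis about food is true. A reader could take that null to mean that training did nothing to food attention. In the other direction, a significant bias score could come from a change in animal gaze with no change in food gaze. A food-only analysis added after the results are known would be post hoc.

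The same gap carries into the models linking attention to eating in the absence of hunger (EAH). They would use pooled gaze or selectivity, while the mediation power statement in section 4 speaks of attention to food cues without defining a measure of it.

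**Working it through.** **The plan's own figure.** Section 4 gives 107 participants, 80% power, two-sided 0.05 and a detectable correlation of 0.27. By Fisher's z, minimum r = tanh((1.960 + 0.842)/√(107 − 3)) = tanh(0.2747) = 0.268. The figure reproduces. It does not bear on this point, except that 107 is used below as the analysed sample.

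**What each outcome estimates.** Let F and A be the mean changes (condition minus control) in gaze to food and to animals.
- Cumulative fixation, pooled: F + A.
- First fixation, pooled: an average over both image types.
- Bias scores: F − A.
- Quantity in the objective: F.

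If F = A, then F − A = 0 whatever the size of F. If F = 0 and A ≠ 0, then F − A ≠ 0. Both statements hold without any assumption about variances.

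**Illustrative power.** Inputs:
- n = 107 (section 4); paired t-test, two-sided 0.05.
- Assumed, because the documents give no gaze SDs or correlations: equal SDs (set to 1) for the food and animal change scores, and correlation ρ between them of 0 to 0.5.
- d = 0.273 for food, chosen because it gives a food-only outcome 80% power at n = 107. That 80% is true by construction.

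Standardised effects:
- pooled = (F + A)/√(2 + 2ρ)
- difference = (F − A)/√(2 − 2ρ)

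For example, if only food moves and ρ = 0.5, pooled = 0.273/√3 = 0.158 (power 37%) and difference = 0.273/√1 = 0.273 (power 80%).

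| True change | Food-only | Pooled, ρ = 0 / 0.3 / 0.5 | Difference, ρ = 0 / 0.3 / 0.5 |
|---|---|---|---|
| Food and animal equally | 80% | 98 / 94 / 90% | 5 / 5 / 5% |
| Animal half as much as food | 80% | 84 / 74 / 68% | 17 / 22 / 29% |
| Food only | 80% | 51 / 41 / 37% | 51 / 66 / 80% |
| Animal only, food unchanged | 5% | 51 / 41 / 37% | 51 / 66 / 80% |

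The 5% entries are the type I error rate. At ρ = 0.7 with only food moving, the pooled outcome has 33% power and the difference 95%.

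The last two rows are identical for the planned outcomes: neither one alone shows whether food gaze or animal gaze changed. The food-only column separates them.

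**The case against.** A reader might infer that attention to food is never tested, or that the second hypothesis has no test at all. The documents do not support that. The bias scores are a valid test of food attention relative to animals, and section 4 repeats all analyses with them, including the attention-EAH models. What is absent is absolute attention to food.

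A reader might also infer that the pooled outcome is the wrong primary. That does not follow either. The first hypothesis in section 2 runs through attention to peripheral cues in general, which the pooled outcome measures. It also has the most power in the case the mechanism predicts: 90-98% when both image types move together, against 80% for food-only.

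The strongest further point is that the plan reports both kinds of outcome, so judging each alone is harsh. With equal SDs the sum and difference are uncorrelated, and the chance that at least one is significant is 1 − (1 − p₁)(1 − p₂). If only food moves, this is 1 − 0.49 × 0.49 = 76% at ρ = 0 and 1 − 0.63 × 0.20 = 87% at ρ = 0.5, unadjusted for two tests. With Bonferroni it is 63-79%. This stands as a limit on the loss of power. It does not supply an estimate of the food effect, and the rate is the same if only animal gaze moved.

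The exactly null bias score is also a limiting case. Section 1 itself suggests that food cues may make different attentional demands from less salient ones. With animal gaze moving half as much as food, the difference score has 17-29% power: low, but not zero. Finally, food-only gaze cannot by itself separate a food effect from general distractibility, which is the reason to keep the bias score.

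**Conclusion.** The concern holds as a mismatch between objective and outcome. Sections 1, 2 and 8 name attention to food; sections 3 and 4 define only pooled gaze and food selectivity. That no food-only outcome is defined follows from the text. That pooling covers both image types is inferred from the distractor wording, but no other reading fits the mixed display and the bias definitions.

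The algebra needs no assumptions: equal changes leave the bias at zero, and a change in animals alone moves it. The power figures are only illustrative. They rest on n = 107, d = 0.273, equal SDs and ρ of 0 to 0.5, with the food-only 80% set by construction. On those terms the pooled outcome falls to 37-51% if only food gaze changes, and the bias score to 5% if both change equally.

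The case is for adding a food-only measure. It is not a case for replacing the pooled primary outcomes, which suit the general-attention step and are stronger when both image types move together.

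**What to change.** In section 4:
- Keep the pooled primary outcomes and the bias scores.
- Add prespecified first fixation duration and cumulative fixation duration on food images, with the same two measures on animal images reported alongside, for each condition contrast (multi-task vs control, sustained attention vs control) and for the attention-EAH models.
- State that the bias score measures food selectivity, and that a null bias score is not evidence of no effect on attention to food.
- Use one term for the comparison image, which section 4 variously calls animal, toy and toy animal.

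Cost: no new data, since the bias scores already require food and animal durations to be scored separately. The downside is a few more tests. They should be labelled as supporting or brought into the multiplicity handling.
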